3. SYNOPSIS

Study Title	A prospective randomised controlled study assessing the impact of simulation training in primary total hip replacement (THR).
Short title	THR Performance & Assessment
Study registration	IRAS Project ID: 270167 6th August 2019
Sponsor	University of Oxford/Clinical Trials and Research Governance Joint Research Office, [name]

Funder	Dinwoodie Charitable Company		
Study Design	Prospective randomised controlled study, with an additional comparator group.		
Study Participants	
Trauma & Orthopaedic Specialty Registrars (intervention and control groups), Consultant Orthopaedic Surgeons, and Arthroplasty Fellows.
 
Patients undergoing elective primary THR at the 2 named NHS Hospitals in this study, when their lead surgeon is enrolled as a participant in this study.
		
Participant Sample Size	
Surgeon participant Group 1 a: Interventional group ('StR's'): Thames Valley Deanery Trauma & Orthopaedic Specialty Registrars on Arthroplasty clinical placements (n=8) receiving additional training
 
Surgeon participant Group 1 b: control group (StR's): Thames Valley Deanery Trauma & Orthopaedic Specialty Registrars on Arthroplasty clinical placements receiving routine and normal Deanery training only (n=8).
 
Surgeon participant Group 2: ('Experts & Fellows'): Consultant Orthopaedic Surgeons (n=5), and nationally appointed Arthroplasty Fellows (n=8).
 
Patient Participants: Estimated total n= 193, calculated on the basis of outcomes data following THR to be collected for:
 
 8 patients per Specialty Registrar (n = 128) 5 patients per Fellow (n = 40) 5 patients per Consultant (n = 25) 		
Planned Study Period	
Total length of project = 18-24 months
 
Length of individual participants involvement = 6 months
		
Planned Recruitment period	
Start date for recruitment = August 2019
 
End date for recruitment = February 2021 (with possible extension to August 2021)
		
	Objectives	Outcome Measures	Timepoint(s)

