7. STUDY DESIGN

Please see Appendix A for study flow diagram.

This is a prospective randomised controlled study designed to assess the impact of specific training interventions on surgical trainee's operative performance and patient outcomes following primary elective THR. We will also study the performance and patient outcomes of both 'Experts' and 'Fellows' in an additional comparator group, which will allow a potential expert standard in THR to be defined.

All study participants will be recruited from 2 Hospitals within the Thames Valley (Oxford) Post-graduate Medical Deanery, and will be composed of: Trauma & Orthopaedic Specialty Registrars ('StRs') holding national training numbers; Consultant Orthopaedic Surgeons ('Experts'); and Orthopaedic Arthroplasty Fellows ('Fellows'). Over the 18-24 month anticipated study period we aim on recruiting a total of up to 16 StR's, 8 Fellows, and 5 Experts. See section 9 for further details on participant recruitment.

StR's will be randomised in a 1:1 ratio to receive either: routine normal Deanery training (the control group, n=8); or routine normal Deanery training with additional simulation-based and cognitive learning (the intervention group, n=8). The intervention group will receive this training for 1-2 hours per week over a 4 to 6-week period. The 'Experts' and 'Fellows' will not be eligible for any intervention, and will act as a separate comparator group.

All participants will be assessed intra-operatively at set timepoints when performing elective primary THR surgery on patients within the named NHS Hospitals. The timepoints will vary depending upon each group. Each StR enrolled into this study will be assessed at a minimum of 8 separate THR operations over a 6-month period, commencing at 6 weeks in to their 6-month clinical placement. Both the 'Fellows' and 'Experts' will be assessed at a minimum of 5 separate THR operations depending upon the reliability of their performance data.

All patients in this study will have been listed for routine elective primary THR surgery under a named Orthopaedic Consultant on the NHS. There will be no interventions or deviations from routine clinical practise regarding the pre-operative investigations or work-up, the operation itself, the peri-operative care, or post-discharge follow-up.

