8. PARTICIPANT & PATIENT IDENTIFICATION

8.1. Consultants, Fellows, and Specialty Registrars

Group 1 ('StR's'): Trauma & Orthopaedic Specialty Registrars on Arthroplasty clinical placements.

Group 2 ('Experts' and 'Fellows'): Consultant Orthopaedic Surgeons, and nationally appointed Orthopaedic Arthroplasty Fellows.

Inclusion Criteria

Group 1 ('StR's'): All Specialty Registrars holding a National Training Numbers (NTN) in Trauma & Orthopaedic Surgery within the Thames Valley (Oxford) Deanery and who are or will be working on arthroplasty clinical placements at either the NOC, Oxford University Hospitals NHS Foundation Trust, or WGH, Buckinghamshire Healthcare NHS Trust over the specified recruitment period will be eligible for participation in this study. We anticipate recruiting 2 StR's from each recruitment centre every 6 months, over an 18 to 24-month period (total n = 12-16).

Group 2 ('Experts' and 'Fellows'): All Consultant Orthopaedic Surgeons with a sub-specialty practise in adult reconstructive (arthroplasty) surgery holding substantive posts at the NOC are eligible for participation in this study. The Consultant Orthopaedic Surgeons at WGH will not be required for the intra-operative assessment within this study, as we will gather sufficient motion data from the NOC Consultants to be able to benchmark an 'expert' performance. Nationally appointed Orthopaedic AF's working at either at either the NOC, Oxford University Hospitals NHS Foundation Trust, or WGH, Buckinghamshire Healthcare NHS Trust over the specified recruitment period will be eligible for participation in this study. We anticipate recruiting 2 AF's every 6-months over an 18 to 24-month period (total n = 6-8)

Exclusion Criteria

- Inability to comply with study procedures or timetable

- Moving outside of the area, relinquishing their position, or National Training Number.

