9.4 Randomisation

Randomisation will be performed via a blinded sealed envelope containing information regarding which arm of the study they will participate in. As we only anticipate recruiting 2 StR's from each recruitment centre every 6 months, a more complex allocation/randomisation procedure will not be required. Over the 18 to 24-month study period we aim to recruit and randomise 6-8 StR's to the 'intervention' group, and randomise 6-8 StR's to the 'control' (routine training) group, with an even distribution of these StR's in both groups across the two recruiting hospital sites.

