11 STATISTICS AND ANALYSIS

Analysis of motion data.

Motion data from the wireless sensors produces performance surrogate markers such as: the number of movements (major & minor); total path length; and smoothness/economy of movement. Data distributions will be assessed for normality using the Shapiro-Wilk test. Previous studies show such data are not normally distributed, and we would expect to use non-parametric tests, such as the Mann-Whitney U test to compare the performance metrics between the 2 groups of participants (StR's against Experts & Fellows). The Mann-Whitney U test will also be used to compare performance metrics between the two sub-groups of StR's (control and intervention), and also within the intervention sub-group in order to compare performance before and after training.

Performance metrics within all groups of participants will be reported using descriptive statistics to outline the central tendency (mean, median, and mode) and variation (range, variance, and standard deviation) in readings obtained. The Kruskal-Wallis one-way analysis of variance (ANOVA) test will be used to test for differences in the mean values obtained for all performance metrics between the two groups of participants. The Wilcoxon signed-rank test will be used to determine any differences in performance metric between the two groups.

Analysis of other routinely obtained data

X-ray (radiograph) analysis:

X-rays will be reviewed by two independent Consultant Orthopaedic Surgeons who will be blinded to the patient and lead surgeon's identity in order to reduce bias. There are several important parameters to be evaluated when reviewing a pelvic x-ray, therefore we will ask each reviewer to allocate a categorical global rating (see below) for both the pre- and post-operative x-rays. [5] The Chi-squared test will be used

to determine if there are any significant differences between each group, and also intra-group differences (for example StR's before and after additional training).

Pre-operative x-ray

- 1: Hip osteoarthritis without significant bone loss.
- 2a: Hip osteoarthritis with significant bone loss on acetabular side.
- 2b: Hip osteoarthritis with significant bone loss on femoral side.
- 3: Hip osteoarthritis with significant bone loss on both acetabular and femoral sides.

Post-operative x-ray

- 1: Excellent implant position and restoration of hip anatomy.
- 2a): Good overall with minor imperfections on acetabular side.

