- 2b): Good overall with minor imperfections on femoral side.
- 3: Moderate concerns but does not require revision surgery.
- 4: Significant concerns requiring revision surgery.

Every patients post-operative x-ray will also be reviewed by the PI ([name]) for acetabular component positioning (inclination and version) using the methodology described by Bachhal [4]. This continuous data will be assessed for normality of distribution, and analysed using similar methodology as described above for the motion data. We will be looking for any statistically significant differences between the 2 groups of participants, within the two sub-groups of StR's (control and intervention), and also within the intervention sub-group in order to compare performance before and after additional training.

Other outcomes data:

Following collection of the outcome measures listed below, the normality of the data distribution will be checked with the Shapiro-Wilk test. Descriptive statistics will be used to outline the central tendency and variation of these data sets. Statistical analyses between each group of participants will be performed using either the parametric unpaired t-test or a non-parametric Mann-Whitney U test depending on the distribution of the data. Subsequent analysis of the outcomes data using a paired t-test, or Mann-Whitney U test will also be performed within the two sub-groups of the StR's (control and intervention), and also within the intervention sub-group in order to compare outcomes before and after additional training.

- Theatre time usage.
- Blood loss (pre-/post-op haemoglobin levels)
- In-patient length of stay.
- PROMs: EQ-5D and OHS.

The Chi-squared test (or Fishers exact test if the sample is <5) will be used to determine any significant differences between the groups regarding the incidence of blood transfusions or peri-operative morbidity.

All of these tests will be performed using the SPSS statistical package, which is available for any registered student on the University of Oxford current Licencing agreement.

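### The registrar arm comparisons leave out hospital, although the plan aims to balance the arms across two hospitals; this can cost power and biases the comparison if the split is uneven

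*Combined protocol and SAP*

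**What the plan says.** **Allocation.** Section 7 states that "StR's will be randomised in a 1:1 ratio to receive either" routine training or routine training plus simulation. Section 8.1 gives the accrual: "We anticipate recruiting 2 StR's from each recruitment centre every 6 months, over an 18 to 24-month period (total n = 12-16". Section 9.4 aims for 6–8 StRs per arm, "with an even distribution of these StR's in both groups across the two recruiting hospital sites". The only mechanism given is this: "Randomisation will be performed via a blinded sealed envelope containing information regarding which arm of the study they will participate in". The section adds that "a more complex allocation/randomisation procedure will not be required".

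**Analysis (section 11).**
- Motion metrics: "The Mann-Whitney U test will also be used to compare performance metrics between the two sub-groups of StR's (control and intervention". Cup inclination and version follow the same approach.
- Theatre time, haemoglobin, length of stay and PROMs: comparisons between participant groups are made "using either the parametric unpaired t-test or a non-parametric Mann-Whitney U test depending on the distribution of the data". For the StR sub-groups the section names a paired t-test or Mann-Whitney, without saying what is paired.
- X-ray grade: chi-squared. Transfusion and morbidity: chi-squared or Fisher.
- GRS, OSATS and checklists: no test is specified.

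Hospital is not mentioned in section 11.

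**The concern.** The two sites belong to different NHS Trusts. Operating time, transfusion, length of stay and the supervising Consultant may all depend on where an StR works, although the documents do not say that they do. With at most 16 randomised surgeons, hospital is one of the few sources of variation that can be removed cheaply.

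If the arms are evenly split over hospitals, an unadjusted test leaves the hospital gap in its error term and is too conservative. If they are not evenly split, part of the gap enters the estimated training effect.

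**Working it through.** **The plan's own figure.** 8×16 + 5×8 + 5×5 = 128 + 40 + 25 = 193 patients, as in the Synopsis, including "8 patients per Specialty Registrar (n = 128". There is no power calculation to reproduce.

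**Inputs.** From the documents: 8 v 8 StRs, two hospitals, 2 StRs per hospital per six months, hence 8 per hospital over 24 months. Assumed, because not stated: one mean per StR, SD 1 between StRs within a hospital, normal data, true effect 1.5 SD, two-sided alpha 0.05, hospital gap g from 0 to 2 SD. Mann-Whitney is unchanged by a log transform, so the results also hold for log-normal data modelled on the log scale.

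**Bias.** The unadjusted arm difference carries (p_I − p_C)·g, where p_I and p_C are the shares of each arm at the first hospital.
- 4/4: (4/8 − 4/8)g = 0
- 5/3: (5/8 − 3/8)g = g/4
- 6/2: (6/8 − 2/8)g = g/2

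**Why an even split makes the test conservative.** Within an arm of 8, the gap adds 8×(g/2)² = 2g² to the sum of squares, so the expected variance estimate is 1 + 2g²/7. That is 1.29 at g = 1 and 2.14 at g = 2. The true SE of the difference is √(2/8) = 0.50, but an unadjusted t-test uses about 0.57 and 0.73. Mann-Whitney behaves in the same way.

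**Simulation, 4/4 split.** Exact Mann-Whitney (reject if U ≤ 13) against a linear model with arm and hospital (16 − 3 = 13 residual df):

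| Gap (SD) | Power, Mann-Whitney | Power, with hospital | Type I, Mann-Whitney |
|---|---|---|---|
| 0 | 77–78% | 79–80% | 5% |
| 0.5 | 75% | 79% | 4.5% |
| 1.0 | 68% | 79% | 3% |
| 1.5 | 56% | 79% | 1.3% |
| 2.0 | 41% | 79% | 0.5% |

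The loss is not peculiar to the rank test: the unadjusted t-test falls from 79% to 71% at 1 SD and 47% at 2 SD. With 6 v 6 (3/3), Mann-Whitney power is 59%, 47% and 23% at gaps of 0, 1 and 2 SD, against about 64% adjusted.

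**Simulation, uneven splits.**
- 5/3, type I error: 3–5% for gaps up to 2 SD, so no inflation.
- 5/3, power, 1 SD gap against the intervention: 51–52% unadjusted, 76–77% adjusted.
- 5/3, power, 1 SD gap favouring the intervention: 82% unadjusted, 77% adjusted.
- 6/2, type I error: 11% at 1 SD and 17% at 1.5 SD, against 5% adjusted.

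**How likely each split is.** Under unrestricted 8-of-16 allocation with 8 StRs per hospital, an a-and-(8 − a) split has probability C(8,a)²/C(16,8), doubled for a ≠ 4, with C(16,8) = 12,870.
- 4/4: 4,900/12,870 = 38%
- 5/3: 2×3,136/12,870 = 49%
- 6/2: 2×784/12,870 = 12%
- 7/1: 2×64/12,870 = 1%

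So 6/2 or worse has a chance of about 13%. Averaged over all splits, the Mann-Whitney type I error stays at about 5%.

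**Price of adjusting.** The arm–hospital correlation is r = 2/8 at 5/3 and 4/8 at 6/2, and the variance of the adjusted estimate is multiplied by 1/(1 − r²) = 1.07 and 1.33. Adjusted power is therefore 77% and 67%, whatever the gap. With no hospital gap, the unadjusted test has about 77% at either split.

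**The case against.** **Section 9.4 states an aim, not a design constraint.** This stands. It describes no stratification, so one cannot say that the analysis omits a formal stratification factor. The power-loss table applies only if balance is reached, by intention or by chance. The case for a hospital term does not depend on that, because an uneven split brings bias instead.

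**A reader might infer that any uneven split creates false positives.** At StR level this is not so. The commonest uneven split, 5/3, gives no inflation, and error averaged over unrestricted allocation is about 5%. If the 128 operations were tested individually, which the plan does not rule out, 5/3 would give about 10% at a 0.5 SD gap and 22% at 1 SD even without clustering. That depends on the unstated unit of analysis, and clustering within StR is a separate fault.

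**The sizes are assumed.** This also stands. Gaps of 1–2 SD are large and have no support in the documents; at 0.5 SD the even-split loss is only about 4 points. Motion metrics come from sensors and the X-ray grades from blinded reviewers, so a hospital effect on how those are measured is not evident.

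**At 5/3 the unadjusted test can look more powerful (82% v 77%).** That happens only when the gap favours the intervention, so the gain is bias and not a reason to leave hospital out.

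**The paired t-test might be meant to pair StRs within hospital.** The plan names no pairing factor, so this cannot be relied on.

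**Conclusion.** The point holds in a limited form. The plan aims for hospital balance, describes nothing that secures it, and uses hospital in none of its specified arm tests.

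Under the assumptions above, the cost with an even split is lost power: small at a 0.5 SD gap, about 11 points at 1 SD (68% v 79%) and 38 points at 2 SD (41% v 79%). With an uneven split the estimate is biased by a quarter of the gap or more. Inflated type I error at StR level is confined to 6/2 or worse.

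The documentary gap and the direction of the effects are firm. The magnitudes are illustrative, because the documents give no hospital difference, SD, effect size, alpha or unit of analysis. The point does not cover GRS, OSATS or checklists, which have no specified analysis, or the comparison of StRs with Experts and Fellows.

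**What to change.** In section 11, replace the unadjusted two-sample test as the main arm analysis.

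- **Continuous outcomes** (motion metrics, cup position, theatre time, haemoglobin change, length of stay, PROMs): one summary per StR, on the log scale where skewed, in a linear model with arm and hospital. As a sensitivity check, permute arm within hospital.
- **Binary and categorical outcomes** (transfusion, morbidity, X-ray grade): compare StR-level proportions with arm permuted within hospital, in place of the unstratified chi-squared or Fisher test. For X-ray grade, state in advance which grades are counted.

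The linear model is preferable to an exact hospital-stratified Wilcoxon test for the main analysis. At 4 v 4 per hospital that test attains an alpha of only 0.0286 and has about 65% power for the same effect.

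**Cost.** A short paragraph, which also settles the StR as the unit of analysis for these comparisons; one degree of freedom; no new data, since hospital is known for every StR. If the split is uneven and the hospitals do not differ, power is about the same at 5/3 (77% v 77%) and lower at 6/2 (67% v 77%).

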6. OBJECTIVES AND OUTCOME MEASURES

Objectives	Outcome Measures	Timepoints of evaluation
Primary To assess the impact of simulation training on surgical trainee performance and patient outcomes following THR.	Participants: 
 Wireless motion data metrics from elbow worn sensors (hand movements, path length and time taken) Global Rating Scales (GRS). Objective Structured Assessment of Technical Skills (OSATS). Surgical checklists. Patients: 
 X-ray analysis of THR.[4] Blood loss and transfusion rates. Peri-operative patient morbidity In-patient length of stay. PROMs: EQ-5D and OHS. 	Intra-operative assessments to be performed at a minimum of 8 separate THR operations for each participant in Group 1 (StR'S) over a 6-month period. Outcome measures data will be collected for all patients who have had a THR performed by any participant as the lead surgeon in this study.
Secondary To define an expert standard when performing a primary elective THR. To determine if operative surgeon performance metrics during a THR relate to surgical experience, or patient outcomes.	Participants: 
 Wireless motion data metrics from elbow worn sensors (hand movements, path length and time taken) Patients: 
 X-ray analysis of THR.[4] Blood loss and transfusion rates. Peri-operative patient morbidity In-patient length of stay. PROMs: EQ-5D and OHS. 	Intra-operative assessments at a minimum of 5 separate THR operations for each participant in Group 2 (Experts & Fellows). Outcome measures data will be collected for all patients who have had a THR performed by any participant as the lead surgeon.

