9.3. Subsequent Visits

Group 1a ('StR's') - Intervention group:

StR's randomised to the 'intervention group' will be required to complete the 4-week period of additional training outlined in section 9.3. Following completion of this additional training, participants within this group will undertake approximately 2 intra-operative assessments every 6 weeks over the duration of their 6-month clinical placements (total 8 assessments). The StR's will also undertake a final Technical Skills assessment in OOSEC Laboratory at 3 months into their placement (See Appendix A for Study Flow Diagram).

Group 1b ('StR's') – control group:

Participants within this group will undertake approximately 2 intra-operative assessments every 6 weeks over the duration of their 6-month clinical placements (total 8 assessments). The StR's will also undertake a final Technical Skills assessment in OOSEC Laboratory at 3 months into their placement (See Appendix A for Study Flow Diagram).

Group 2: 'Experts' and 'Fellows':

Following enrolment for participation in this study, all participants within this group will undergo a baseline practical skills assessment within the OOSEC. Participants within this group will then undertake a minimum of 5 separate intra-operative assessments each.

Patients:

Following enrolment for participation in this study, all patients will be asked to complete the pre-operative PROMs questionnaires (EQ-5D and OHS). These are part of routine clinical care, and are a mandatory for all patients undergoing THR in the NHS. The patients will not be asked to undertake any further assessments outside of their routine clinical care until the time of their scheduled post-operative out-patient department (OPD) clinic review appointment. All patients will only be followed up routinely following discharge by their named Consultant in an OPD clinic. This OPD appointment normally takes place 6 to 8 weeks following discharge. No additional clinic appointments or investigations will be required outside of the patients expected routine clinical care. At this visit the patients will be asked to complete the post-operative validated PROMs questionnaires (EQ-5D and OHS). This takes a few minutes and is the only extra outcome measure the patients are asked to complete.

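### Section 11 does not say how each registrar's 8 operations enter the arm comparison, so the deciding contrast is open and no planned analysis shows whether a training effect changes over the placement

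*Combined protocol and SAP*

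**What the plan says.** Section 7 states: "All participants will be assessed intra-operatively at set timepoints when performing elective primary THR surgery". For every registrar it has assessment "commencing at 6 weeks in to their 6-month clinical placement". Section 9.3 gives the pace in both registrar arms: "approximately 2 intra-operative assessments every 6 weeks over the duration of their 6-month clinical placements (total 8 assessments"; for the intervention arm only, it ties the start to the end of training: "Following completion of this additional training, participants within this group will undertake approximately 2 intra-operative assessments every 6 weeks". The objectives table in section 6 gives only the overall span: "Intra-operative assessments to be performed at a minimum of 8 separate THR operations for each participant in Group 1 (StR'S) over a 6-month period".

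For motion metrics, section 11 compares the registrar arms in one sentence: "The Mann-Whitney U test will also be used to compare performance metrics between the two sub-groups of StR's (control and intervention". It does not say whether the data are the first operations, the last, all of them, or one score per registrar. Cup position is to be "analysed using similar methodology as described above for the motion data". The other continuous outcomes get a t-test or Mann-Whitney test, again without a time element. The only time-related contrast is "also within the intervention sub-group in order to compare performance before and after training", which is not an arm comparison over the placement. The stage timings in section 9.7 are times within one operation, not operation order.

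**The concern.** The trial pays for repeated assessment over months, but the analysis plan does not say how the repeats are used. Both arms keep operating after a short course, so a benefit that shrinks as controls gain experience is plausible. If it does shrink, the first operations, the last operations and the average answer different questions and have very different power. With no contrast named, the choice can be made after the data are seen. No planned analysis would show a changing effect.

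There is a second consequence. Without a registrar-level summary, the literal way to run a two-sample test is on every operation, treating 8 operations by one surgeon as 8 independent observations. That rejects too often. Naming a single primary outcome would settle neither matter.

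**Working it through.** **Inputs from the documents.** 8 v 8 registrars (sections 3 and 7), or 6 to 8 per arm (section 9.4); 8 operations each at about 2 per 6 weeks (section 9.3). The plan's counts reproduce: 16 × 8 = 128 registrar operations, and 128 + 8 × 5 + 5 × 5 = 193 patients. The pace gives 8 / 2 = 4 windows, or 24 weeks.

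**Assumed, because the documents give none.** Two-sided 5% level; single-operation SD of 1; ICC (correlation between operations by the same registrar) of 0.1 to 0.5; effects as stated below.

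**Start of assessment.** Taking 6 months as 26 weeks, a week-6 start leaves 20 weeks: 20 / 6 = 3.3 windows, or 6.7 operations at the stated pace. Eight operations do not quite fit unless assessment runs past the placement or the pace rises.

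**All operations treated as independent, no true effect.** The variance of the arm difference is understated by 1 + 7 × ICC. The approximate rejection rate is 2 × [1 − Φ(1.96 / √(1 + 7 × ICC))].

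| ICC | 1 + 7 × ICC | 1.96 / √ | Rejection rate |
|---|---|---|---|
| 0.1 | 1.7 | 1.50 | 13% |
| 0.3 | 3.1 | 1.11 | 27% |
| 0.5 | 4.5 | 0.92 | 36% |

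Simulating the Mann-Whitney test on 64 v 64 operations gives 13% to 35% over this range. One mean per registrar holds about 5%.

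**Choice of contrast under a fading benefit.** Assume 1.2, 0.8, 0.4, 0 SD over the four windows (mean 0.6, change 0.4 per window), with t-tests on registrar summaries (14 df). The noncentrality is d / (SD × √(2/8)). At ICC 0.3:

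- SD of a 2-operation mean: √(0.3 + 0.7/2) = 0.806. First window: 1.2 / 0.403 = 2.98, power 79%. Last window: d = 0, rejection 5%.
- SD of an 8-operation mean: √(0.3 + 0.7/8) = 0.622. Average: 0.6 / 0.311 = 1.93, power 43%.
- SD of a registrar's slope per window: √((0.7/2)/5) = 0.265. Trend: 0.4 / 0.132 = 3.02, power 80%, if all registrars learn at the same rate.

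Across ICC 0.1 to 0.5 the average has 68% down to 32% power, and the trend 70% up to 91%. In simulation at ICC 0.3, the first window, last window and average do not all agree on significance in 79% of trials. First and last are significant in opposite directions in only about 1%.

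With 6 v 6 (√(2/6), 10 df, ICC 0.3) the noncentralities are 2.58, 1.67 and 2.62, giving power of about 64% (first), 33% (average) and 66% (trend).

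**Cross-check with Mann-Whitney on registrar means.** A steeper assumed fade (1.5, 1.0, 0.5, 0 SD) at ICC 0.3 to 0.7 gives 84% to 92% on the first window, 36% to 59% on the average and about 5% on the last.

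**Constant effect of 1 SD, ICC 0.3.** Average 85%, any single window 64%. First, last and average still disagree on significance in 42% of trials.

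**Free choice, no true effect.** At least one of the four windows or the average is significant in 0.19, 0.17 and 0.14 of trials at ICC 0.1, 0.3 and 0.5.

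**Trend test when learning rates differ.** Assume a between-registrar SD of 0.5 or 1.0 in first-to-last change. With no arm effect, an interaction test using only a random intercept rejects in about 8% or 15% of trials. A comparison of per-registrar slopes remains valid, but its power against the 1.2-to-0 fade drops to 68% or 46%. With a milder fade (1.0 to 0.4 SD) it has 28% power even when learning rates are equal.

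**The case against.** The fairest defence is that section 9.3 states a pace, not analysis windows, that section 6 frames assessment as at least 8 operations over 6 months, and that the plainest reading of section 11 is one comparison using all of them. The flow diagram in Appendix A, not shown in the text available, may define the timepoints, although it is unlikely to state an analysis contrast. Much of this stands. But using all operations does not say whether they enter as 64 v 64 values or as one mean per registrar, and the working shows that this matters.

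Several stronger readings are tempting, and the documents do not support them:

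- That early, late and averaged results would give opposite answers. Under a simple fade they differ in significance; opposite direction needs a true reversal.
- That the plan has a 14% to 19% false-positive rate from testing windows. The plan proposes no such search; the figure measures the freedom left to the analyst.
- That the course comes before the placement, making a large early gap natural. Sections 7 and 9.6 suggest that training runs inside the placement while both arms operate.
- That ignoring operation order in itself biases the comparison. It does not if both arms keep the same schedule.
- That operation dates are already held for analysis. Section 12 lists no operation date or sequence number among the items to be extracted.

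It is also fair to say that naming the average does not rescue a fading benefit, and that part of the repair is the ordinary correction for repeated operations within a surgeon.

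**Conclusion.** The point holds as a gap in specification. Section 11 leaves the summary over the 8 operations undefined, uses neither operation order nor registrar, and plans nothing that would show a changing effect; no other section fills this. Under the assumed fade at ICC 0.3, power runs from 5% to 79% depending on which operations are used. Pooled as independent, the stated test has a true error rate of 13% to 35% at assumed ICC 0.1 to 0.5. The count of four windows is inferred from the stated pace. The effect sizes, ICCs, 5% level and learning-rate variation are all assumptions, so the figures show how much the open choice could matter. They do not predict this trial's results.

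**What to change.** In section 11:

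1. Make the deciding arm contrast the difference averaged over each registrar's 8 operations, analysed at registrar level. Use either one mean per registrar (which allows a t-test or Mann-Whitney test on 8 v 8), or a mixed model on a suitably transformed metric with a random registrar effect and small-sample degrees of freedom. Say how the average is formed when a registrar has more or fewer than 8 operations.
2. Add operation number and operation date to the recorded data.
3. Add one supportive analysis of arm by operation number, using a random registrar slope or a comparison of per-registrar slopes, not a random intercept alone. Show the estimated arm difference early and late, with intervals.
4. State that windows will not be tested separately.

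Reconcile sections 7 and 9.3 on when assessment starts in each arm. If the starts differ, the same operation number would fall at a different point of the placement in each arm.

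The cost is wording, two recorded fields and slightly more analysis; no extra participants or operations are needed. The supportive trend test has limited power with 12 to 16 registrars and cannot by itself declare success. The average gives the best power for a constant effect but only modest power for a fading one, and section 11 should say so.
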